## 5. GENERAL METHODOLOGY AND CONVENTIONS

The primary analysis will be performed when all randomized participants have either completed their 12-week study participation period or withdrawn early, or the study stop prematurely due to any reason, and the database is released.

### 5.1. Hypotheses and Decision Rules

Statistical inference will be made on the primary endpoints: IGA/PGA success rate at Week 12. The null hypothesis is that there is no difference between any PF-07038124 doses being tested and vehicle. The alternative hypothesis is that at least one PF-07038124 dose being tested is superior to vehicle with a higher IGA/PGA success rate. The study will be considered positive for each indication when the corresponding null hypothesis is rejected. For each indication, the overall family wise Type I error rate will be controlled at 1-sided 0.025 level using the Hochberg step up procedure.

A sufficient number of AD participants will be screened to achieve approximately 120 participants randomly assigned to study intervention. The sample size calculation is based on the primary efficacy estimand IGA success at Week 12. Assuming 15% IGA success rate for the vehicle arm, a sample size of 40 per arm will have 89% power to detect a treatment difference of 35% under a 1-sided type 1 error 0.0125 for each of the 2 dose levels comparison to vehicle by the unconditional exact test, with an overall Type 1 error 0.025 1-sided. In addition, this sample size will provide 96% power to detect a 42% difference in EASI-75 between an active arm (62% EASI-75) and vehicle (20% EASI-75).

A sufficient number of PsO participants will be screened to achieve approximately 120 participants randomly assigned to study intervention. The sample size calculation is based on the primary efficacy estimand PGA success at Week 12. Assuming 8% PGA success rate for the vehicle arm, a sample size of 30 per arm will have 92% power to detect a treatment difference of 42% under a 1-sided type 1 error 0.008 for each of the three dose levels comparison to vehicle by the unconditional exact test, with an overall Type 1 error 0.025 1-sided. In addition, this sample size will provide 96% power to detect a 44% difference in PASI-75 between an active arm (50% PASI-75) and vehicle (6% PASI-75).

## **5.2. General Methods**

### **5.2.1. Analyses for Binary Endpoints**

For landmark (cross-sectional) analyses of binary endpoints, Blyth-Still-Casella method will be used for estimates and confidence interval for each treatment arm, and Chan and Zhang's exact confidence interval (CI) method will be used for differences between treatment arms.

For all binary endpoints, a summary of number and percentage of participants in each category by treatment arm and time will be produced and the response rate will also be plotted against time by treatment.

### **5.2.2. Analyses for Continuous Endpoints**

Landmark (cross-sectional) analyses of key continuous endpoints will be performed by analysis of covariance (ANCOVA). The ANCOVA model will include treatment arm as fixed effect and baseline dependent variable as a covariate. Estimates of least square mean (LSM) values and the LSM differences between each PF-07038124 dose and vehicle will be derived. The corresponding p-values and 95% confidence intervals will also be presented.

Mixed model repeated measures (MMRM) models may be used when there are multiple time points. The fixed effects of treatment, visit, and treatment by visit interaction will be included. Baseline value will be included as a covariate. Unstructured covariance matrix will be assumed for the model errors when possible. Compound symmetry covariance matrix

will be used if the model with unstructured covariance doesn't converge. At each visit, estimates of least square mean (LSM) values and the LSM differences between each PF-07038124 dose and vehicle will be derived. The corresponding p-values and 95% confidence intervals will also be presented.

Unless stated otherwise, descriptive summary statistics of absolute values, change and percent from baseline for all continuous variables will be presented by treatment and time. These statistics will include n, mean, median, standard deviation, minimum and maximum.

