### **6.2.2. Continuous Secondary Endpoints**

Continuous secondary endpoints include percent CFB in EASI total score, CFB in PASI total score, and percent CFB in affected BSA.

- Estimand strategy: Secondary estimand ([Section 2.2.2](#)). This estimand is intended to provide an estimate of the treatment effect in the absence of prohibited medication use in a population that may or may not be fully compliant with the treatment.
- Analysis set: ITT Analysis Set ([Section 4](#)).
- Analysis methodology: A landmark analysis of these continuous endpoints at Week 12 will be performed by ANCOVA with baseline as a covariate. Missing data, except missing due to COVID-19 pandemic, will be imputed using a control-based imputation method. PROC MI will first be called to impute missing vehicle observations under the assumption data are missing at random (MAR) and impute

missing active treatment observations assuming they are similar to corresponding vehicle arm. The imputation will utilize ANCOVA model including baseline as a covariate fitted using only vehicle arm data. The analysis will combine the results from the multiple imputations using Rubin's rule's as implemented in SAS PROC MIANALYZE. MMRM models may also be used on observed data at all time points as sensitivity analyses. The fixed effects of treatment, visit, and treatment by visit interaction will be included. Baseline value will be included as a covariate. No adjustments for multiplicity will be made.

- Intercurrent events and missing data: A) Prohibited medication: all scores measured at time points after start date of the event for participants who receive prohibited medication post randomization will be excluded from the analysis and treated as missing scores. Missing scores will be imputed. B) Withdrawal and all other events leading to missing data, except COVID-19 pandemic: all missing scores will be imputed. C) COVID-19 pandemic: if a participant misses a visit due to COVID-19, he/she will be excluded from the analysis for that visit; If a participant discontinues treatment or withdraws from the study due to COVID-19, he/she will be excluded from the analyses after the treatment discontinuation visit or study withdrawal visit, respectively. D) Inadequate compliance – participants data will be used as recorded.

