### Sample SAS Code for Estimand 2 MMRM

```
proc mixed data=_dsnin order=internal alpha=<Value>;  
  by PARAMN;  
  class SUBJID AVISITN TRTPN;  
  model PCHG = BASE TRTPN AVISITN TRTPN*AVISITN /solution ddfm=kr;  
  repeated AVISITN/ participant =SUBJID type=un r rcorr;  
  /**try UN first, if not converged, will use CS***/  
  lsmeans TRTPN*AVISITN / diff cl alpha=<Value>;  
  ods output lsmeans=lsmeans diffs=diffs;  
run;  
/*For one-sided P-value calculation, the LOWER tail side should be used. */;
```

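### Compound symmetry as the only fallback can misstate the Week 12 standard error in the optional MMRM sensitivity analysis of EASI and PASI

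*SAP*

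**What the plan says.** SAP 5.2.2 sets the first choice: "Unstructured covariance matrix will be assumed for the model errors when possible". It then names a single alternative: "Compound symmetry covariance matrix", which "will be used if the model with unstructured covariance" does not converge. The MMRM sample code in SAP Appendix 4 carries the same rule as a comment: "try UN first, if not converged, will use CS". Neither place names a structure between the two.

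The model line in that code is "model PCHG = BASE TRTPN AVISITN TRTPN*AVISITN /solution ddfm=kr". Standard errors are therefore model-based with the Kenward-Roger adjustment. The procedure call has no empirical (sandwich) option.

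The role of the model is limited. For the continuous secondary endpoints, SAP 6.2.2 states: "A landmark analysis of these continuous endpoints at Week 12 will be performed by ANCOVA with baseline as a covariate", with control-based multiple imputation for missing values. On the repeated-measures model it says: "MMRM models may also be used on observed data at all time points as sensitivity analyses". SAP Appendix 1 agrees: ANCOVA is the secondary analysis at Week 12, and MMRM on observed cases is the sensitivity analysis. When the MMRM is run, SAP 5.2.2 calls for LS mean differences, p-values and 95% intervals at each visit.

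**The concern.** Compound symmetry assumes one variance for all visits and one correlation for all pairs of visits. The modelled outcomes are change (PASI) and percent change (EASI) from baseline. Both are zero for everyone at Day 1, so it is plausible that their spread differs between Week 1 and Week 12. If it does, a model-based standard error under compound symmetry is wrong at individual visits, and nothing in the code guards against this.

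What is at stake is the value of the sensitivity analysis. Its purpose is to show whether the imputed Week 12 ANCOVA result stands up on observed data. Intervals that are too narrow would give false reassurance, and intervals that are too wide would give false doubt. Earlier visits matter a little as well. EASI and PASI change are secondary endpoints at all scheduled visits, while SAP Appendix 1 lists ANCOVA for them at Week 12 only. SAP 5.3.1 does mention landmark analyses by week, so the MMRM is not necessarily the only source of results for those visits.

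**Working it through.** **No figure to reproduce.** Neither document gives an SD by visit, an expected interval width or any other number for the MMRM. The SD patterns below are assumptions, and only their shape matters.

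**Inputs from the documents.** The post-baseline treatment visits are Weeks 1, 2, 4, 6, 8, 10 and 12 (protocol Schedule of Activities), which makes seven. There are 40 participants per arm in three arms for AD and 30 per arm in four arms for PsO (SAP 5.1). The confidence level is 95% (SAP 5.2.2).

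**Formulas.** Take complete, balanced data with a treatment-by-visit model, and ignore the small contribution of the baseline covariate:

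- Compound-symmetry SE of the Week 12 difference = sqrt(2 × mean visit variance / n).
- Unstructured SE of the same difference = sqrt(2 × Week 12 variance / n).
- Ratio r = sqrt(mean visit variance) / Week 12 SD. The sample size cancels.
- Actual coverage of a nominal 95% interval = 2Φ(1.96 r) − 1.

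For a linear pattern from a at Week 1 to b at Week 12, the SD at week w is a + (b − a)(w − 1)/11.

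**Worked example, SD 35 to 45.** The seven SDs are 35.00, 35.91, 37.73, 39.55, 41.36, 43.18 and 45.00. Their squares sum to 11,102, so the mean variance is 11,102/7 = 1,586 and its root is 39.83. Then r = 39.83/45 = 0.885, so the SE is about 12% too small. Coverage is 2Φ(1.96 × 0.885) − 1 = 91.7%.

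| Assumed SD, Week 1 to Week 12 | Root of mean variance | r at Week 12 | Coverage |
|---|---|---|---|
| Flat at 30 | 30.00 | 1.00 | 95.0% |
| 35 to 45 | 39.83 | 0.885 | 91.7% |
| 30 to 45 | 37.37 | 0.83 | 89.6% |
| 20 to 45 | 32.84 | 0.73 | 84.7% |
| 25 to 35 | 29.88 | 0.85 | 90.6% |
| 20 to 35 | 27.50 | 0.79 | 87.7% |
| 15 to 40 | 28.05 | 0.70 | 83.1% |
| 35 down to 25 | 30.52 | 1.22 | 98.3% |
| Peak in mid-treatment (25, 30, 35, 35, 33, 31, 28) | 31.19 | 1.11 | 97.1% |

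The direction reverses in the last two rows. The interval is too narrow only when Week 12 variance exceeds the average over visits.

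**Early visits.** With the 35 to 45 pattern the Week 1 ratio is 39.83/35 = 1.14, so the Week 1 interval is too wide. With 20 to 45 it is 32.84/20 = 1.64.

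**Simulation check** (4,000 trials per pattern, complete data). With compound symmetry and AD/PsO arm sizes, coverage at Week 12 was:

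- flat: 95.1/94.8%
- 25 to 35: 90.8/90.9%
- 20 to 35: 88.9/88.1%
- 15 to 40: 83.8/82.5%
- falling: 98.3/98.0%
- mid-treatment peak: 96.8/96.7%

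For the three patterns ending at 45, simulated with three arms of 40 only, it was 92%, 90% and 84%. When the Week 12 variance itself was used, coverage was 94.7% to 95.7% in every pattern in the list.

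**How often the fallback might apply.** An unstructured matrix for seven visits has 7 × 8/2 = 28 parameters (8 × 9/2 = 36 if the follow-up visit is included), against about 120 participants per indication. Failure to converge is possible but is not the expected case.

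**The case against.** A reader might infer that the trial's Week 12 intervals for EASI and PASI will be too narrow. The documents do not support that, for two reasons.

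First, the direction is not known. No SDs by visit are given, and a late fall in spread is plausible on the plan's own figures. Percent improvement in EASI cannot exceed 100%, and SAP 5.1 assumes a 62% EASI-75 rate in an active arm. That would put 62% of the arm between 75% and 100% improvement. If Week 12 variance is below the visit average, the fallback gives intervals that are too wide.

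Second, the reported Week 12 result is a single-visit ANCOVA, which involves no between-visit covariance matrix. For the Week 12 MMRM interval to be too narrow, three things must all happen: the MMRM is run, the unstructured fit fails, and Week 12 variance exceeds the average.

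It would also be wrong to turn these coverage figures into an inflated trial error rate. Formal inference rests on IGA/PGA success, and the continuous secondary endpoints carry no multiplicity adjustment.

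The common baseline slope across visits might seem a second fault. No harm from it has been quantified. The sample MMRM code models percent change, which is already scaled by baseline.

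Finally, SAP 5.2.2 requires descriptive SDs by treatment and time, so marked differences in spread would be visible. These objections limit the point but do not remove it. The fallback rule gives a wrong standard error at Week 12 whenever that visit's variance differs from the average, in either direction. Descriptive SDs would reveal this but not correct it.

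**Conclusion.** The point holds as a minor, conditional improvement. If the optional MMRM is run and the unstructured model fails, the prescribed fallback can misstate the Week 12 standard error. Over the rising patterns tried it is about 12% to 30% too small, with coverage of roughly 92% down to 83%. With a flat SD there is no error. With falling or mid-peak patterns it is 11% to 22% too large.

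These sizes rest on assumed SDs and complete data. With dropout, compound symmetry also weights earlier visits differently and can shift the estimate itself; that effect was not quantified.

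The Week 12 ANCOVA, the primary IGA/PGA analysis and type I error control are unaffected.

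**What to change.** In SAP 5.2.2 and the MMRM code in Appendix 4, replace the single fallback with a fixed sequence after the unstructured matrix: heterogeneous Toeplitz, then heterogeneous first-order autoregressive (ARH(1)), then heterogeneous compound symmetry. Use the first that converges. All three give each visit its own variance, can be used with Kenward-Roger, and deal with rising and falling variance alike.

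If plain compound symmetry is kept as a last resort, pair it with empirical (sandwich) standard errors. Name the degrees-of-freedom method for that step too, because Kenward-Roger adjusts the model-based covariance.

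The cost is a little more text and code; data collection and the other analyses do not change. Fixing the order in advance also removes any choice of structure after the data are seen. A baseline-by-visit term may be added if wanted, but this point does not need it.

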### **5.2.3. Analyses for Categorical Endpoints**

A summary of number and percentage of participants in each category will be presented by treatment and time point.

### **5.2.4. Analyses for Time-to-Event Endpoints**

NA.

## **5.3. Methods to Manage Missing Data**

### **5.3.1. Efficacy Data**

Analysis of binary data including primary endpoints will use the primary estimand (E1). All missing values, except missing due to COVID-19 pandemic, will be set to a failure ([Section 6.1.1](#)).

Continuous secondary endpoint analysis will use the secondary estimand (E2). For each landmark analysis (e.g., cross sectional analysis by week) missing data, except missing due to COVID-19 pandemic, will be imputed using a control-based imputation method ([Section 6.2.2](#)).

Summaries of tertiary/exploratory continuous data will use the observed data only and no additional considerations are needed.

If a participant misses a visit due to COVID-19, he/she will be excluded from the analysis for that visit; If a participant discontinues treatment or withdraws from the study due to

COVID-19, he/she will be excluded from the analyses after the treatment discontinuation visit or study withdrawal visit, respectively.

### **5.3.2. Pharmacokinetic Concentrations and Biomarker Data**

- Concentrations outside the limit of quantification.**

In summary statistics for pharmacokinetic and biomarker data, assayed values below the lower limit of quantification (LLOQ) will be set to zero. Other imputations (e.g.,  $\frac{1}{2}$  LLOQ) may also be considered in other analyses (e.g., Pop-PK and PK/PD analyses), if deemed appropriate. In listings, values below LLOQ will be reported as “<LLOQ” where LLOQ will be replaced with the numerical value for the lower limit of quantification. The LLOQ for various PK and biomarker concentrations will be noted in all tables and listings.

- Missing concentrations.**

If a concentration value is not collected or cannot be analyzed due to sample quality issues, it will be considered as missing data and will not be imputed.

- Missing actual sampling time.**

If actual sampling time (date or hour) value is missing, the protocol-stated nominal time will be used.

## **6. ANALYSES AND SUMMARIES**

### **6.1. Primary Endpoint(s)**

#### **6.1.1. Main Analysis**

- Estimand strategy: Primary Estimand ([Section 2.2.1](#)). This estimand is intended to provide an estimate of the treatment effect in the absence of prohibited medication use in a population that may or may not be fully compliant with the treatment.
- Analysis set: ITT Analysis Set ([Section 4](#)).

- Analysis methodology: A landmark analysis of the IGA/PGA success endpoints at Week 12 will be performed using the ITT analysis set. The proportions responding and the corresponding risk difference comparing active treatment arm to vehicle group will be analyzed using the unconditional exact method; the risk differences and the corresponding 2 sided unconditional exact 95% confidence intervals will be computed using Chan and Zhang (1999) method. The overall family wise Type I error rate will be controlled at the 1 sided 0.025 level using the Hochberg step up procedure.
- Intercurrent events and missing data: A) Prohibited medication – response will be considered as failure for time points after start date of the event for participants who receive prohibited medication post randomization. B) Withdrawal and all other events, except COVID-19 pandemic, leading to missing data will be treated similarly assuming that participants no longer receive benefit from the study intervention and hence will be considered as failure. C) COVID-19 pandemic: if a participant misses a visit due to COVID-19, he/she will be excluded from the analysis for that visit; If a participant discontinues treatment or withdraws from the study due to COVID-19, he/she will be excluded from the analyses after the treatment discontinuation visit or study withdrawal visit, respectively. D) Inadequate compliance – participants data will be used as recorded.
- Proportions, risk differences and 95% confidence intervals will be presented.

### **6.1.2. Sensitivity/Supplementary Analyses**

#### **Sensitivity Analyses:**

If there are enough data in each of the disease severity groups, Cochran test stratified by baseline disease severity with the minimum risk weights proposed by Mehrotra and Railkar (2000) may be considered for IGA/PGA success at week 12.

In addition, a generalized linear mix model may be used for the repeated measures of IGA/PGA success at all time points. The fixed effects of treatment, visit, treatment by visit interaction be included in the model. If there are enough data in each of the disease severity

group, baseline disease severity may be included as additional fixed effect. Unstructured covariance will be used when possible. At each visit, estimates of mean odds ratio between the active treated group and the placebo will be presented. The corresponding p-values and 95% confidence intervals will also be derived from the model.

### **Supplementary Analyses:**

For PGA success data with three active dose levels, a Bayesian Emax model may be used to characterize the dose response relationship ([Appendix 2](#)).

## **6.2. Secondary Endpoint(s)**

### **6.2.1. Binary Secondary Endpoints**

IGA/PGA success at other timepoints, EASI/ PASI-75, PP-NRS success ( $\geq 4$  points of reduction from baseline), IGA/PGA of clear or almost clear will be analyzed the same way as described in [Section 6.1.1](#). PP-NRS success rate will be summarized for all participants in ITT Analysis Set in AD, and adult participants (18–75 years old) only in ITT Analysis Set for PsO.

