### **5.1.2. Disease-Specific Inclusion Criteria:**

#### **5.1.2.1. AD Specific Inclusion Criteria**

4. Have been diagnosed with AD for at least 3 months prior to Screening.

**Note:** The clinical diagnosis of AD will be confirmed according to the criteria of Hanifin and Rajka ([Appendix 10](#)).

5. Have an IGA score of 2 (mild), or 3 (moderate) at Screening and Day 1, prior to randomization. Refer to [Section 8.1.1.1.1](#) and [Appendix 12](#) for the assessment of 5-point IGA.
6. Have AD covering 5% and up to 40% of BSA (excluding the hair-bearing scalp) at Screening and Day 1, prior to randomization. Refer to [Section 10.12.1.3](#) ([Appendix 12](#)) for detailed methods of calculating treatable % BSA.
7. Have a PP-NRS average score of  $\geq 2$  assessed at Day 1, prior to randomization.

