#### **5.1.2.2. PsO Specific Inclusion Criteria**

8. Have a diagnosis of PsO (psoriasis vulgaris) for at least 6 months prior to Screening.
9. Have a PGA score of 2 (mild), 3 (moderate), or 4 (severe) at Screening and Day 1, prior to randomization. Refer to [Section 8.1.2.1.1](#) and [Appendix 12](#) for the assessment of 5-point PGA.
10. Have PsO covering 2% to 20% (inclusive) of BSA (excluding the hair-bearing scalp, palms, soles, finger nails and toe nails) at Screening and Day 1, prior to randomization. Refer to [Section 10.12.2.3](#) ([Appendix 12](#)) for detailed methods of calculating treatable BSA.

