#### 8.1.1.2.1. PP-NRS

The PP-NRS is a daily patient-reported assessment of intensity of pruritus on an 11-point numerical rating scale, with a 24-hour recall period. The PP-NRS will be completed QD, starting at least 7 days prior to Day 1 and then, completed QD every day from Day 1 to Week 12 before study intervention dose is applied, preferably at the same time of each day, as noted in the [SoA](#). All participants will complete the questionnaire at the follow-up visit in clinic.

Note that the average of 7 days (minimum of 4 days) of PP-NRS scores immediately preceding randomization will be used to calculate the baseline average score and assess eligibility, as in [Section 5.1](#).

[figure not shown]
CCI

CCI

CCI

CCI

CCI

- The PP-NRS and **CCI** questionnaires will be completed at the participants' home/residence, using the e-diary provided by sponsor. The PP-NRS will be completed only by participants 18 to 75 years old at Screening, starting from at least 7 days prior to Day 1.

CCI

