### 3.2. Secondary Endpoint(s)

#### For AD:

- Proportion of participants achieving EASI-75 (75% improvement from baseline) at all study visit time points specified in the SoA.
- Proportion of participants achieving IGA score of clear (0) or almost clear (1) (on a 5-point scale) and a reduction from baseline of  $\geq 2$  points at all study visit time points specified in the SoA, except at Week 12.
- Percent CFB in EASI total score at all study visit time points specified in the SoA.
- Proportion of participants achieving IGA score of clear (0) or almost clear (1) at all study visit time points specified in the SoA.
- Proportion of participants having  $\geq 4$  points of reduction from baseline in weekly averages of PP-NRS at study visit time points specified in the SoA.
- Percent CFB in affected BSA at all study visit time points specified in the SoA.
- Incidence of treatment emergent AEs and SAEs, clinically significant changes in vital signs, ECG, and laboratory tests.
- Incidence of increase in local tolerability severity grades at times indicated in the SoA.

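### The 4-point PP-NRS response counts participants whose baseline itch is below 4 and who cannot respond, which shrinks the itch effect and costs power

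*SAP*

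**What the plan says.** SAP 3.2 defines the AD itch endpoint as the proportion with at least 4 "points of reduction from baseline in weekly averages of PP-NRS at study visit time points specified in the SoA". The PsO endpoint is the same, in adults aged 18-75.

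On the denominator, SAP 6.2.1 states for AD that "PP-NRS success rate will be summarized for all participants in ITT Analysis Set in AD". PsO uses adults aged 18-75 "only in ITT Analysis Set for PsO". SAP Appendix 1 repeats the ITT population with non-responder imputation. Neither place sets a condition on baseline itch.

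The entry criteria do not supply one at a useful level:

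- **AD (Protocol 5.1.2.1, criterion 7):** "Have a PP-NRS average score of $\geq 2$ assessed at Day 1, prior to randomization".
- **PsO (Protocol 5.1.2.2):** the criteria cover diagnosis, body surface area and global severity ("Have a PGA score of 2 (mild), 3 (moderate), or 4 (severe) at Screening and Day 1, prior to randomization"), with nothing on itch.

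The scale is described in Protocol 8.1.1.2.1: "The PP-NRS is a daily patient-reported assessment of intensity of pruritus on an 11-point numerical rating scale".

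**The concern.** A participant who enters with an average of 3 can lose all itch and still be counted as a failure, because the largest possible fall is 3 points. The same holds for every baseline below 4. These outcomes are fixed before the first dose and carry no information about treatment.

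The other visible binary efficacy endpoints do not have this feature. Entry at IGA or PGA of 2 or more makes a 2-point fall to clear or almost clear possible for everyone, and EASI-75 and PASI-75 are relative to each participant's own baseline.

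Two things are at stake. The reported itch response rate and risk difference come to depend on how many low-itch participants the sites happen to enrol, which makes them hard to compare between the two indications or with another trial. In addition, the comparison can lose power. Randomisation is stratified by disease severity and tape-strip participation (Protocol 4.1), with no itch stratum visible, so a chance imbalance in the share below 4 also enters the contrast.

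**Working it through.** **Inputs from the documents.** The response threshold is 4 points (SAP 3.2 and 6.2.1) and the scale has 11 points, taken as 0-10 (Protocol 8.1.1.2.1). The arms are 40 for AD and 30 for PsO (SAP 5.1). The method is that of the primary analysis, the unconditional exact test (SAP 6.1.1 and 6.2.1). Secondary binary endpoints have no multiplicity adjustment (Protocol 9.3.2), so 1-sided 0.025 is used.

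**Inputs assumed.** The share f with baseline below 4, and the response rates p1 (active) and p0 (vehicle) among those able to respond. The documents give none of these.

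**Step 1: reproduce the stated powers.** An exact unconditional test (score-statistic ordering, size maximised over the common rate, power by full enumeration) gives:

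| Case | Stated | Recomputed |
|---|---|---|
| AD IGA success, 50% vs 15%, 40/arm, 1-sided 0.0125 | 89% | 88.7% |
| PsO PGA success, 50% vs 8%, 30/arm, 1-sided 0.008 | 92% | 92.5% |

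The method therefore matches the one behind the sample size.

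**Step 2: dilution.** In all participants the rates are (1-f)p1 and (1-f)p0, so the risk difference is (1-f)(p1-p0). With 50% vs 20%:

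- f = 20%: 40% vs 16%, a difference of 0.8 × 30 = 24 points.
- f = 30%: 35% vs 14%, a difference of 0.7 × 30 = 21 points.
- f = 40%: 30% vs 12%, a difference of 0.6 × 30 = 18 points.

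**Step 3: power.** All participants (n per arm, diluted rates) against the restricted set (n(1-f) per arm, undiluted rates), at 50% vs 20%:

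| | f | All participants | Baseline of at least 4 |
|---|---|---|---|
| AD, 40/arm | 20% | 65.6% | 71.8% (32/arm) |
| | 30% | 57.3% | 64.9% (28/arm) |
| | 40% | 48.7% | 58.0% (24/arm) |
| PsO, 30/arm | 20% | 52.5% | 58.0% (24/arm) |
| | 40% | 38.4% | 47.2% (18/arm) |

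**Step 4: sensitivity to the assumed rates.**

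| Scenario | All participants | Baseline of at least 4 |
|---|---|---|
| AD, 80% vs 40%, f = 30% | 71.9% | 87.3% |
| AD, 50% vs 15%, f = 30% | 74.6% | 81.4% |
| AD, 45% vs 20%, f = 30% | 44.0% | 50.6% |
| AD, 25% vs 5%, f = 40% | 46.1% | 46.1% |
| PsO, 30% vs 10%, f = 20% | 37.1% | 37.0% |

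**Why the gain varies.** Under a normal approximation with unpooled variance, the ratio of squared test statistics (all participants to restricted) is S/(S + fQ), where S = p1(1-p1) + p0(1-p0) and Q = p1² + p0².

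- 50% vs 20%, f = 30%: S = 0.25 + 0.16 = 0.41 and Q = 0.25 + 0.04 = 0.29, so the ratio is 0.41/(0.41 + 0.087) = 0.82.
- 30% vs 10%, f = 20%: S = 0.21 + 0.09 = 0.30 and Q = 0.09 + 0.01 = 0.10, so the ratio is 0.30/(0.30 + 0.02) = 0.94.

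The ratio is always below 1, so on this approximation restriction never loses information. At low response rates the loss is small enough for the discreteness of the exact test to mask it.

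**The case against.** The strongest reply is that the SAP does what the estimand says. PP-NRS response is assigned to E1, whose population is the enrolled one, and the all-participant proportion is a legitimate quantity for that population. Participants below 4 are balanced between arms on average, so type I error is not inflated and the attenuation is conservative. On this view, restricting the denominator answers a different question rather than correcting an error. That description is fair, and it is why the all-participant rate should stay in the report. It does not make a responder rate informative when part of its denominator could never respond.

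Other points that stand:

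- The size rests on assumed inputs. At low response rates the power gain is close to nil, so a claim that restriction always raises power would be too strong.
- Restriction recovers only part of the loss. With nobody below 4, AD power at 50% vs 20% would be 81%. At f = 30% it is 57% in all participants and 65% restricted; the remaining gap comes from having fewer people who can respond.
- The endpoint is secondary, with no stated power or multiplicity control, and no visible decision rule uses it.
- The PsO figures use 30 per arm, although the 18-75 age limit may make that set smaller.
- Tertiary and PRO sections are partly redacted, so a restricted itch analysis may exist there. None is visible for the secondary endpoint.

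**Conclusion.** The concern holds. As written, the itch endpoint includes participants who are certain non-responders, and its risk difference is multiplied by (1-f) in both indications. That follows from the definitions and needs no assumption beyond the 0-10 range and some enrolment below 4.

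The size is an assumed range. At 50% vs 20% among those able to respond and f of 20% to 40%, the difference falls from 30 points to between 24 and 18. The recoverable power is about 6 to 9 points in AD and 5 to 9 in PsO. It is larger at high response rates and roughly nil at low ones; in the scenarios examined, restriction never cost more than 0.1 point. The primary analysis and sample size are unaffected. This is a change the plan should make, though no primary conclusion depends on it.

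**What to change.** In SAP 3.2, 6.2.1 and Appendix 1, define the main analysis of 4-point PP-NRS response in randomised participants whose baseline weekly average is at least 4 (for PsO, adults aged 18-75 meeting the same condition). Keep the E1 rules for intercurrent events and missing data, and report the all-participant rate as supportive.

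Two details should be settled in the same edit:

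- **Baseline rule.** Protocol 8.1.1.2.1 asks for at least 4 of the 7 days for the AD baseline average. SAP 3.4 averages whatever was recorded from Day -7 to Day -1, with no minimum. The SAP should say which rule decides membership of the subset, for both indications, and how a missing baseline is handled.
- **Record of the change.** SAP 2.1 lists no modifications to the protocol's analysis. The new population for this endpoint should be entered there and in the E1 description in SAP 2.2.1.

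The cost is SAP wording only, with no new data or visits. The subset is defined by a measure taken before dosing, so the randomised comparison is preserved. The downside is a smaller denominator (24 per arm in AD and 18 in PsO at f = 40%), which in the scenarios examined the larger contrast offsets or outweighs. The change should be fixed before unblinding; made later, the same analysis would be post hoc.
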